**The Effect of On-site CT-derived Fractional
Flow Reserve on the Management Making for
the Patients With Stable Chest Pain
(TARGET Trial)**

NCT number: NCT03901326

Date of the document : 08/20/2020

1 **STUDY PROTOCOL**

2

3 **The Effect of On-site CT-derived Fractional Flow Reserve on the Management Making for the**
4 **Patients With Stable Chest Pain (TARGET Trial)**

5

6

7 **Background**

8 Coronary computed tomographic angiography (CCTA) has become an excellent rule-out test for suspect
9 coronary artery disease (CAD). The recommendation for CCTA was even expanded by one national
10 guideline as a first-line test to patients with intermediate and high likelihood of CAD based on their
11 cost-effectiveness analysis suggesting that this would be a lower-cost strategy. However, the relative low
12 specificity of CCTA in the diagnosis of functional myocardial ischemia makes it difficult to act as a real
13 gate- keeper for the patients to be referred to invasive coronary angiography (ICA). In developing countries
14 like China, for the patients with prior CCTA test who are subject to downstream ICA, over 30% of them
15 were found to have no obstructive CAD. Even more, the invasive procedure seems to be much more
16 frequent when CCTA was introduced to clinical practice in some pragmatic clinical trials.

17 Recently, CT-FFR, a kind of novel functional assessment derived from CCTA, dramatically increases
18 the specificity of diagnosis on flow-limiting coronary stenosis, enabling CCTA to become a more robust
19 non-invasive strategy. It showed a great potential in detecting functional myocardial ischemia related to
20 coronary-specific lesion (in Discovery-Flow, DEFACTO, and NXT trials). Moreover, clinical care guided
21 by CT-FFR could provide benefits with equivalent clinical outcomes and lower expenditure, compared with
22 routine clinical care over 1-year follow-up (Platform trial). In addition, ADVANCE study revealed that
23 CT-FFR modified the treatment recommendation which might reduce unnecessary ICA, predict
24 revascularization, and further identify subjects at low risk of adverse events through 90 days.

25 However, these studies were not randomized designed and selection bias still existed. Also, the
26 cost-effectiveness of CT-FFR in clinical practice remains to be determined, especially in developing
27 countries. The purpose of this present study will be to evaluate whether CCTA/CT-FFR outperforms the
28 usual care in ruling out patients without significantly obstructive CAD before invasive catheterization and
29 improving clinical prognosis during follow-up in a randomized design.

30 **Method/design**

[figure not shown]
31 **Study aim**

32 TARGET trial is a multicenter, prospective, open-label, and pragmatic randomized controlled trial
33 evaluating the effect of a CCTA/CT-FFR strategy (group A) on management decision making versus usual
34 care (group B) in intermediate-to-high risk patients with suspected CAD who undergo clinically indicated
35 diagnostic evaluation. Recruitment commenced in August 2019. The schedule of enrollment and
36 assessments follows the SPIRIT Figure. The study protocol (Version 3.0/201812) and other relevant
37 documentations have been approved by the institutional human research ethic committee of Chinese PLA

38 General Hospital and the relevant national ethics committees as well as registered on ClinicalTrials.gov
39 identifier: NCT03901326.

40 **Setting**

41 This multicenter randomized controlled clinical trial will be carried out in 6 tertiary hospitals across China,
42 all of which has the volume of over 200 patients in outpatient area of cardiology division each working day.
43 Participating subjects will be enrolled and subsequently assigned to either usual care group or CT-FFR care
44 group via computer-generated random numbers (1:1 ratio) (Figure 1). The trial accords with the SPIRIT
45 guidelines. The treatments (both intervention and control) will be delivered by licensed clinicians in the
46 participating sites. Central telephone is used for allocation of sequence. Participants will be randomized to
47 the CT-FFR examination group or usual care group using a randomization procedure. The cardiologist will
48 be aware of patients' group allocation because they will provide the trial intervention, but they will not be
49 involved in the analysis. Participants are not blind to their group allocation, nor are their physicians who are
50 informed of screening results of their patients (if the patient consents) and give the recommendation by
51 outpatient or telephone. There will be no special criteria for discontinuing or modifying allocated
52 interventions.

53

54 **Figure 1: The flow chart of TARGET trial.**

55

56 **Eligibility criteria**

57 **Inclusion criteria**

58 Consecutive patients with new-onset chest pain suspicious for CAD will be included. Subjects with

59 intermediate-to-high pretest probability of CAD will be recruited based on the CAD Consortium basic
60 pretest probability score. Another major inclusion criterion is the CCTA result which showed that the
61 diameter stenosis is between 30 and 90% in at least one major coronary artery (coronary artery diameter \geq
62 2.5 mm).

63 The typicality of the chest pain was determined by three characteristics of chest pain, including
64 central chest discomfort lasting below 15min, provoked by exertion or emotional stress, and relieved by
65 rest or nitrates. This definition is similar with the NICE guideline update (2016). Non-anginal pain was
66 defined as the presence or absence of only one characteristic of chest pain. Atypical angina was defined as
67 the presence of two characteristics. Agreement to participate in this trial will be necessary and informed
68 consents will be obtained from all subjects before recruiting.

[figure not shown]
69 **Exclusion criteria**

- 70 a. Diagnosed or suspected acute coronary syndrome requiring hospitalization or emergent testing;
- 71 b. Hemodynamically or clinically unstable condition systolic blood pressure < 90 mmHg or serious atrial
72 or ventricular arrhythmias;
- 73 c. Known CAD with prior myocardial infarction, percutaneous coronary intervention (PCI), coronary
74 artery bypass graft (CABG), or any angiographic evidence of $\geq 50\%$ stenosis in any major coronary
75 artery;
- 76 d. Patients with left main branch stenosis $\geq 50\%$ or one major coronary stenosis $> 90\%$ by CCTA;
- 77 e. Known severe congenital, valvular (moderate and above), or cardiomyopathy process (hypertrophic
78 cardiomyopathy or reduced systolic left ventricular function $\leq 40\%$) which could explain cardiac
79 symptoms;
- 80 f. Unable to provide written informed consent or participate in long-term follow-up.

81 **Measurement**

82 CCTA image is obtained before the patient's first visit and assessment. When subjects are randomized to
83 the CT-FFR arm, on-site FFR based on the CCTA imaging (DEEPVESSEL FFR, Beijing CuraCloud
84 Technology Co., Ltd., Beijing, China) will be measured. DEEPVESSEL FFR workstation is very
85 dedicated software utilizing the original CCTA imaging to meter simulated FFR values based on a
86 machine learning algorithm, which has been introduced in previous articles. The calculation process could
87 be summarized as follows: the first step is to extract a 3D coronary artery model and generate coronary
88 centerlines which are similar to the routine reconstruction of CCTA. A modified 3D U-Net like model is
89 employed to generate a major coronary artery tree followed by a graph cut to refine the boundary of the
90 arteries. The center-lines are extracted using a minimal path extraction filter. Then, a novel path-based
91 deep learning model, referred to DEEPVESSEL FFR, is used to predict the simulated FFR values on the
92 vascular center-lines. Deep learning algorithm is used to establish characteristic sample database of
93 coronary hemodynamic characteristic parameters. When the deep training model is proved to be valid, it is

94 applied to a new lesion-specific measurement. DEEPVESSEL FFR system consists of a multi-layer
95 perceptron network (MLP) and a bidirectional multi-layer recursive neural network (BRNN). The whole
96 model can process variable-length input, and each point of the input sequence is transferred separately
97 corresponding to MLP; the output of the MLP is transferred into the BRNN to optimize the sequence
98 model. In comparison with the previous technology, the major advantage of DEEPVESSEL FFR model is
99 more accurate because of the incorporation of context information on target FFR along the vessel path.
100 More specifically, DEEPVESSEL FFR workstation includes the neural networks set on each point of the
101 vascular path. Structural and functional features of each point on the vascular centerlines are considered as
102 input, while calculating FFR of each point as output. Therefore, DEEPVESSEL FFR is on the coronary
103 tree simultaneously at a quick time at post-processing (**Figure 2**). Lesion-specific CT-FFR is defined as
104 simulated FFR value at distance of 20mm away from the lesion of interest.

105
106 **Figure 2: Schematic presentation of DEEPVESSEL FFR measurement on coronary artery stenosis**
107

108 If the subjects are randomly allocated to CT-FFR arm, they will be examined by DEEPVESSEL FFR
109 for three major epicardial arteries. If the result of CT-FFR calculation is less than or equal to 0.8 in one or
110 more major, coronary arteries, the patient will be referred to ICA directly; if the result of CT-FFR value is
111 more than 0.8, optimal medical therapy will be recommended. The decision on the mode of
112 revascularization is left to the treating cardiologists and depends on local practice standard.

113 Correspondingly, if the subjects are randomized to usual care arm, attending physicians will decide
114 the next step of diagnosis and treatment, such as exercise ECG, stress cardiac echo, cardiac MR, and
115 SPECT. According to the results of examination combined with risk factors assessment and clinical
116 manifestations, physicians should provide recommendation whether the subjects would undergo ICA or
117 not. The evaluation criteria of functional examination include but not all:

118 a. The exercise ECG criterion for a positive test is greater ≥ 1 mm of horizontal or down sloping ST
119 segment deviation (depression or elevation) in any lead except aVR for at least 60 to 80 ms after the end

120 of the QRS complex, either during or after exercise;

121 b. The nuclear cardiology criterion for a positive result is evaluated as follows: perfusion is graded using a
122 5-point scale (0 to 4) in each of 20 myocardial segments. Summed rest scores, summed stress scores,
123 and summed difference scores (SDS) are recorded. Reversible defects are graded as small if SDS was 2
124 to 4, moderate if SDS was 5 to 8, or large if SDS was > 8. Subjects are categorized as having ischemia
125 if more than 1 of the following criteria was present: SDS was ≥ 2 and/or there was an ungated
126 stress-and-rest volume (transitory ischemic dilation) ratio of > 1.19 ;

127 c. The stress cardiac echo criterion for a positive result is evaluated as follows: abnormal findings
128 include those with fixed wall-motion abnormalities or new or worsening abnormalities indicative of
129 ischemia. A segment with resting dysfunction may show either a sustained improvement during stress
130 indicating a non-jeopardized myocardium (stunned) or improve during early stress with subsequent
131 deterioration at peak (biphasic response). The biphasic response is suggestive of viability and
132 ischemia, with jeopardized myocardium fed by a critically coronary stenosis. Resting wall motion
133 abnormalities, unchanged with stress, are classified as “fixed” and most often represent regions of
134 prior infarction.

135 The DICOM imaging data will be transferred to on-site workstation to complete DEEPVESSEL FFR
136 measurement and the on-site lab will provide the report to the referral physician within 24 h for decision
137 making.

138 On the consent form, participants will be asked if they agree to use of their data should they choose
139 to withdraw from the trial. Participants will also be asked for permission for the research team to share
140 relevant data with people from the hospital taking part in the research, where relevant. This trial does not
141 involve collecting biological specimens for storage.

142 **Downstream decision making**

143 The results of the index test will be provided to the reference cardiologist of the patients’ institution who
144 will make clinical decisions based on the integrated evaluation of patient clinical assessment and index
145 test findings. Optional use of invasive FFR or intravascular imaging (IVUS or OCT) and the decision on
146 the mode of revascularization are left to the interventional cardiologists and depends on local practice
147 standard.

148 At baseline, 6 months, and 12 months, recommendations for therapy are made in line with guidelines
149 published. The goal of anti-hypertensive therapy is to achieve a blood pressure of less than 140/90 mmHg.
150 The choice of anti-hypertensive therapy will be left to the treating physician. The aim of anti-lipid therapy
151 is to achieve levels of LDL $< 1.9\text{mmol/l}$. In the first instance, statin therapy will be initiated and then
152 increased with the addition of a second agent if necessary. In the case of diabetics with a raised blood
153 sugar, the primary health care physician is asked to measure HbA1c and to ensure that the patients’
154 subsequent therapy is tailored to achieve a HbA1c of less than 6.5mg/dl. Smokers are referred to the

155 smoking cessation clinic.

156 **Follow-up**

157 Subjects will be contacted regularly by trained interviewers at 90 days, 3 months, 6 months, and 12
158 months post-enrollment for follow-up assessment until death, withdrawal, or end of the trial (**Figure 3**).

159 All subjects are followed for a minimum of 12 months. An independent clinical event adjudication
160 committee (CEC) reviewed all primary endpoint event and secondary endpoints in a blinded fashion. The
161 decisions of CEC will be used to implement the final statistical analysis.

Time point	STUDY PERIOD					
	Enrollment visit	Allocation	Intervention	3months± 7days	6months ± 7days	1 year ± 7days
Eligibility screen	×					
Informed consent	×					
Demographic data	×					
Allocation		×				
Diagnosis			×			
Conventional Coronary Angiography			×	×		
Coronary revascularization			×	×	×	×
MACE				×	×	×
AE				×	×	×
Medical cost				×	×	×
Quality of life				×	×	×
Radiation exposure				×	×	×

162 **Figure 3:** Chronology of the research (Standard Protocol Items: Recommendations for Interventional
163 Trials (SPIRIT) Figure)

164

165 The data were collected, coded, and entered by the trial investigators, and the paper-based CRF form
166 is sent to the trial office by investigators to ensure that the data would not be tampered. The researchers
167 used double data entry and range checks for data value method to ensure the accuracy of the data. A
168 clinical research organization (CRO) has been contracted to oversee the monitoring of all sites,
169 establishing the eCRF and checking the completeness and consistency of the trial data. Adherence to this
170 trial will be monitored via hospital information system. The follow-up examination results should be sent
171 to the research site, and the examination results of the grade 3 hospital can be accepted to maintain the
172 credibility.

173 **Endpoint of the study**

174 The primary endpoint of the present trial is comparison between the two arms in the rate of planned ICA
175 without significant obstructive CAD or interventions within 90 days. Significant obstructive CAD is
176 defined as more than or equal to 70% of diameter stenosis by quantitative coronary analysis in core lab or
177 invasive FFR ≤ 0.8 if available during procedure. Interventions includes stent implantation, balloon
178 dilation and bypass surgery.

179 The secondary endpoint will be the comparison between the two treatment arms in terms of MACE,
180 quality of life, cumulative effect dose of radiation exposure, and overall cardiac medical cost during the
181 follow-up at 1 year.

183 The Seattle Angina Questionnaire (SAQ-7) was used to assess the clinical effect and quality of life
184 (QOL). We will also measure the cumulative radiation exposure dose (ED) over the entire study period by
185 assessing the original average dose for each test performed during the follow-up. In case the ED for each
186 test is not known, we will use the standard ED available for each test in the literature.

187 Major adverse cardiovascular events (MACE) will be defined as a combined endpoint of (a)
188 hospitalization for unstable angina, (b) revascularization by PCI or CABG after 90 days, (c) non-fatal MI,
189 and (d) cardiac death: any death because of immediate cardiac cause (e.g., MI, low- output failure, fatal
190 arrhythmia) or vascular cause (e.g., cerebrovascular disease, pulmonary embolism, ruptured aortic
191 aneurysm, dissecting aneurysm, or other vascular cause). Unwitnessed death and death of unknown cause

217 choose to withdraw from the trial. Participants will also be asked for permission for the research team to

218 share relevant data with people from the hospital taking part in the research, where relevant. This trial
219 does not involve collecting biological specimens for storage. At present, there is no plan to share the data
220 with other teams or organizations. The datasets analyzed during the current study are available from the
221 corresponding author on reasonable request.

222 Results will be disseminated via a peer-reviewed report to the sponsor, which will be freely available,
223 and through open access journal articles and conference presentations. Standard journal authorship criteria
224 will apply; there will be no use of professional writers.

225 Informed consent forms are available from the corresponding author on request. If it is necessary to
226 amend protocol, we will notify the sponsor and funder first then the primary investigator will notify the
227 centers, and a copy of the revised protocol will be sent to the primary investigator to add to the
228 Investigator Site File. Any deviations from the protocol will be fully documented using a breach report
229 form, and the amendment of protocol will be updated in the clinical trial registry.

230 **Ethics statement**

231 The study protocol is complied with the World Medical Association Declaration of Helsinki. Ethical
232 clearance for the TARGET trial has been obtained from the ethical committee of Chinese PLA general
233 hospital.

234 **Ethics approval and consent to participate**

235 The study protocol has been approved by the ethics committee of Chinese PLA general hospital and other
236 5 participating sites, including Qilu Hospital of Shandong University, Anzhen Hospital Capital Medical
237 University, First Affiliated Hospital of Xinjiang Medical University, Second Affiliated Hospital School of
238 Medicine Zhejiang University and Tongji Hospital Tongji Medical College Huazhong University of
239 Science and Technology. We will obtain written informed consent from each patient before they are
240 randomized. Participants may withdraw from the trial at any time for any reason.

241

242 **Sample size calculation**

243 The sample size is defined based on the rate of planned ICA without significant obstructive CAD within
244 90 days. Based on previous data and assuming the prevalence of non-obstructive CAD or intervention
245 during ICA in usual care group is about 30%. The frequency of reduction in the primary endpoint is
246 expected to be 30% for a \geq 90% power. Considering a drop-off up to 10%, the final overall population
247 should be of 1216 patients.

248 **Statistical analysis plan**

249 Baseline characteristics will be presented. Continuous variables were described as mean \pm Standard
250 deviation (SD) or median (interquartile range), and compared between the groups using either Student's 2
251 sample t- test for paired or nonparametric Wilcoxon rank sum test. Categorical variables were summarized as
252 counts (percentages) and compared using the Pearson chi-square test or Fisher exact test if cell frequencies

253 were insufficient. Kaplan-Meier survival curves and Cox-regression modelling will be used for time to event
254 outcomes. The patient reported outcomes, such as Seattle Angina Questionnaire, will be compared between
255 the two groups using 2 sample t-test. The total cardiac costs will be compared using nonparametric Wilcoxon
256 rank-sum test) or a 2 sample t-test based on means of log transformed costs between the two groups, because
257 of the expected skew in cost data. The hazard ratio (HR) is presented as 95% confidence intervals (CI). P <
258 0.05 is considered as significance in statistics. Because there are no anticipated problems that are detrimental
259 to the participants, interim analyses and formal stopping procedure are not necessary for this trial. Missing
260 values will be managed by using multiple imputation. If there is any non-adherence with the trial protocol
261 and intervention plan, investigators will record it truthfully. Intention-to-treat analysis will be applied for
262 patients who do not adhere to the intervention. In addition, all efficacy analyses were performed on a
263 per-protocol set that excluded patients with major protocol deviations. Based on the data of the current study,
264 further subgroup analysis will be conducted for the additional purpose in the future.

265

266 **Analysis and reporting Plan**

267 **1. Disposition of the study population**

268 A clear account of all patients who entered the trial will be produced. Withdrawal information including
269 the primary reasons of discontinuation will be summarised and presented by group.

270 **2. Protocol deviations**

271 A listing of all Major or Potential/Serious Breach (Major protocol deviations with potential to affect
272 patient safety/data) and Potential/Serious Breach (Major, Potential or Serious Breach of GCP guidelines or
273 consistent non-compliance by site) will be produced (by patient and site where applicable).

274 **3. Baseline and demographic characteristics and Treatment information (ITT population)**

275 Summary statistics will be produced and presented by group for demographic and baseline
276 characteristics, comparisons will be undertaken to investigate clinical importance of any imbalance.

277 **4. Primary outcome (ITT population)**

278 The primary endpoint of the present trial is comparison between the two arms in the rate of ICA
279 without significant obstructive CAD or intervention within 90 days. The significant obstructive CAD is
280 defined as more than or equal to 70% DS by quantitative coronary analysis or invasive FFR \leq 0.8, if
281 available during the procedure. Intervention includes stent implantation, balloon dilation and bypass
282 surgery. This result will be showed by a Figure.

283 **5. Secondary outcome: clinical outcomes (ITT population and PP population)**

284 For the comparison of clinical outcomes between the two groups at 1 year. The number and
285 proportion of experiencing at least one event, including: (a) hospitalization for unstable angina, (b)
286 revascularization by PCI or CABG after 90 days, (c) non-fatal MI, and (d) cardiac death: any death
287 because of immediate cardiac cause) will be reported and presented by group. Time to the first clinical
288 event will be described using Kaplan Meier plots, presented by arm, and analysed using Cox regression

289 modelling.

290 **6. Secondary outcome: medical cost outcomes (ITT population)**

291 Total medical costs over 12 months of follow-up will be measured for each patient by sum of the
292 numbers of key medical resources used between study entry and the 12 months follow-up point. The
293 CT-FFR assessment is free during the trial, but the cost of CT-FFR will be add in the analysis based on a
294 uniform market price once obtained. The total cardiac medical costs over follow-up will be compared
295 between the two arms in an intention-to-treat fashion. The mean and median cost should be presented and
296 compared in the two randomly assigned groups. The total cardiac cost was compared using a two-sample
297 t-test after a log transformation if skew distribution of the data was found. If the distribution remains
298 right-skewed after log transformation, a non-parametric Mann-Whitney tests will be needed to test the
299 hypotheses that nine month costs differ between groups.

300 **7. Secondary outcome: patient reporting outcome (ITT population)**

301 For the questionnaire patient reported endpoints (Seattle Angina questionnaire-7) at 12 months, change
302 scores from baseline to 12 months will be presented and mean (or median) change from baseline to 9
303 months will be compared between groups using t-tests (or the Wilcoxon rank-sum test), where
304 appropriate.

305 **8. Secondary outcome: radiation exposure outcome (ITT population)**

306 The cumulative radiation exposure dose (ED) over the entire study period will be reported by
307 assessing the original average dose for each test performed during the follow-up. In case the ED for each
308 test is not known, we will use the standard ED available for each test in the literature.

309 **9. Safety reporting (ITT population and PP population)**

310 CCTA related serious adverse events will be recorded and summarized if any. A listing of serious
311 adverse events will be provided for all related/unrelated SAEs.

312 **10. Other analyses (ITT population and PP population)**

313 If differences on the primary outcome are observed between groups, exploratory analyses into
314 revascularization rate to determine what the drivers are will be carried out. Some results of diagnostic
315 Strategy during initial management, as well as invasive coronary angiography, will be showed by tables
316 and.

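### Cheap, modest improvement (not an error): the primary endpoint has no planned effect measure or confidence interval, and CCTA stenosis, pretest probability and site go unused

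*Combined protocol and SAP*

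**What the plan says.** Item 4 of the Analysis and reporting Plan is headed "4. Primary outcome (ITT population"). It restates the endpoint and its definitions and closes with "surgery. This result will be showed by a Figure". It names no test, model, effect measure, interval or covariate.

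The Statistical analysis plan section has one rule that fits a binary outcome. Categorical variables are summarised as "counts (percentages) and compared using the Pearson chi-square test or Fisher exact test if cell frequencies" are too small. The rule follows the sentences on baseline characteristics, so it reaches the primary endpoint only by being general. The one interval mentioned is "The hazard ratio (HR) is presented as 95% confidence intervals (CI"), and Cox modelling is reserved for time-to-event outcomes. On missing data, the section says that missing "values will be managed by using multiple imputation".

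Three baseline variables are available. Under Inclusion criteria, CCTA diameter stenosis (30 to 90%) and the CAD Consortium basic score decide eligibility. Under Measurement, the CCTA precedes the first visit. Under Setting, the trial "will be carried out in 6 tertiary hospitals across China", and allocation is 1:1 with no stratification factor named. No planned analysis uses these variables as covariates. Item 3 only compares baseline characteristics between the groups, with no rule for what follows if they differ.

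**The concern.** MACE, a secondary endpoint, has a planned model and an effect measure with an interval. The primary endpoint has neither. Reported strictly to plan, the main result would be two percentages, a P value and a figure. Readers would have no planned statement of how precisely the difference is known, which matters in a pragmatic comparison of two strategies.

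The choice among risk difference, risk ratio and odds ratio, and between adjusted and unadjusted analysis, would also stay open until the data are seen. The baseline comparison in item 3 could then prompt adjustment after the fact. Naming the covariates in advance closes that route and may buy a little precision.

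**Working it through.** **Inputs from the documents** (Sample size calculation; Statistical analysis plan): control rate 30%; 30% reduction, read as relative, giving 21%; power at least 90%; significance level 0.05, taken as two-sided; 10% drop-off; total 1216; 1:1 allocation.

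**The plan's own figure.** The pooled two-proportion formula is n = [1.96·√(2·0.255·0.745) + 1.2816·√(0.30·0.70 + 0.21·0.79)]² / 0.09² = 491 per arm, or 982 in total. Dividing by 0.9 and rounding up per arm gives 1092; a continuity correction gives 1140. The stated 1216 is not reproduced, but it errs on the safe side. That is a separate matter.

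**Unadjusted analysis.** Evaluable patients: 1216 × 0.9 / 2 = 547 per arm.
- SE of the difference = √[(0.2100 + 0.1659)/547] = 0.02621. Half-width = 1.96 × 0.02621 = 5.14 points.
- Null SE = √(2·0.255·0.745/547) = 0.02636. Power = Φ[(0.09 − 1.96·0.02636)/0.02621] = Φ(1.46) = 92.8%.
- The result that the plan does not ask for would, at the design rates, be a risk difference of −9.0 points (95% CI −14.1 to −3.9), or a risk ratio of 0.70 (0.57 to 0.86).

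**Adjusted analysis.** R² is the share of outcome variance that the covariates explain. The documents give none, so it is assumed. As an approximation, variance is multiplied by (1 − R²) and half-width by √(1 − R²).

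| Assumed R² | Power | Half-width (points) |
|---|---|---|
| 0 | 92.8% | 5.14 |
| 0.02 | 93.3% | 5.09 |
| 0.05 | 94.0% | 5.01 |
| 0.10 | 95.0% | 4.87 |
| 0.20 | 96.9% | 4.60 |

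**Simulation check.** 6000 trials per scenario; logistic model with arm, stenosis category, pretest score and site, averaged to a risk difference. Assumed: stenosis categories 30–49/50–69/70–90% holding 35/40/25% of patients; site shares 30/22/17/13/10/8%.

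| Scenario (assumed) | Power, unadjusted to adjusted | Adjusted half-width (unadjusted 5.13) |
|---|---|---|
| R² 0 | 93.1 to 92.9% | 5.14 |
| R² about 0.02, risk highest in the middle stenosis category | 92.9 to 93.3% | 5.08 |
| R² about 0.05, risk falling with stenosis | 93.2 to 93.9% | 5.00 |
| R² about 0.10, as above with a strong site effect | 92.7 to 94.9% | 4.86 |
| R² about 0.04, no site effect | 92.2 to 93.4% | 5.03 |

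Type I error of the adjusted test was 5.0 to 5.4% (Monte Carlo SE 0.3). A further 3000-run simulation with stronger assumed covariates moved power from 92.7 to 94.7% at R² 0.07 and from 92.8 to 96.1% at R² 0.16. With 608 per arm, about 10% of outcomes missing and 20 imputations, coverage was 94.5 to 94.8% and null rejection 4.6 to 5.6% in the two scenarios tried.

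**Lower control rates** (assumed, same relative reduction). Unadjusted power is 85.9% at 25% and 75.3% at 20%. Simulated adjusted power is 85.3 to 88.2% and 76.1 to 80.0%.

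**The case against.** The strongest reply is that adjustment is a preference. The unadjusted test is valid, power on the stated inputs already exceeds 90%, and at these gains no decision is likely to change. That stands, and it is why the point is modest.

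The covariates may also be weak. Lower stenosis may make ICA less likely but a non-obstructive finding more likely once ICA is done, and the two can offset. In the CT-FFR arm referral follows the 0.8 cut-off, so the relation may differ by arm. The scenario with risk highest in the middle category gained only 0.4 points of power, and about half of the largest R² came from the assumed site effect. This also stands. It argues for categorical stenosis and a robust interval, and against promising more than a small gain.

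Four stronger readings are tempting, and the documents do not support them:
- *The primary analysis is wrong.* It is not: the general rule supplies a valid test.
- *The size of the effect would go unreported.* The planned arm percentages give the point difference by subtraction, and the counts would let a reader compute an interval. What is missing is a named measure and a prespecified interval.
- *The change is free.* Recruitment began in August 2019, so it means amending an ongoing trial. The schedule lists an eligibility screen but does not say which values are recorded.
- *Adjustment protects the trial if the control rate is lower.* The last calculation shows that it does not restore 90%.

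A related question is whether the 30% applies to all randomised patients. The text says "The sample size is defined based on the rate of planned ICA without significant obstructive CAD within" 90 days, but words the rate as one "during ICA in usual care group is about 30" per cent. If only ICA patients were the denominator, the figures here would describe a different quantity. That question is larger than this one and should be raised separately. The ITT heading of item 4 supports the all-randomised reading used here.

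**Conclusion.** The point holds as a cheap, modest improvement. The part that needs no assumption is that no effect measure or confidence interval is planned for the primary endpoint. The part that rests on assumption is the gain from adjustment: about 0 to 2 points of power over 92.8%, with the half-width falling from 5.14 to 4.87 points at an assumed R² of 0.10 and not at all at R² = 0. A larger gain, about 4 points, would need an R² near 0.20, for which the documents offer no evidence. All figures assume 30% v 21% among all randomised patients, a two-sided 5% level and 547 evaluable per arm. This is worth doing before analysis, but the planned test would not be invalid without it.

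**What to change.** Add to item 4 of the Analysis and reporting Plan:

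> Primary analysis, in all randomised patients by assigned arm: standardised risk difference (CT-FFR minus usual care) with robust 95% CI and P value, from a logistic model with arm, maximum CCTA stenosis (categorical), pretest probability and site. A patient followed to day 90 with no ICA counts as no event. A patient lost before day 90 with no ICA recorded has a missing outcome, which is multiply imputed as planned. Supporting analysis: unadjusted risk difference with 95% CI and chi-square test.

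The stenosis cut-points should be fixed at the same time, since the documents give only the 30 to 90% range; so should a fallback, such as dropping site, if the model does not converge. If the sponsor does not want an adjusted primary analysis, the minimum is one sentence specifying the unadjusted risk difference with its 95% CI.

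The cost is a protocol/SAP amendment before analysis, with the notification and registry update described under Date management and organization, and one regression model. No new visits or procedures are needed, provided that the stenosis and pretest values used for eligibility are held in the trial data. That should be confirmed first.
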